3.3.3. Risk assessment, study conduct and method of dose escalation

3.3.3.1. Number of subjects receiving the study drug simultaneously

To minimize the risk to healthy volunteers, the administration of the investigational product in each dose group of the study will be done sequentially within each cohort:

Table 7 Cohorts and treatment doses.

Cohort	Treatment dose (randomization)
1 (8 subjects)	Single oral administration of DNDI-6148, 10 mg on Day 1 or placebo (6/2)
2 (8 subjects)	Single oral administration of DNDI-6148, 20 mg on Day 1 or placebo (6/2)
3 (8 subjects)	Single oral administration of DNDI-6148, 40 mg on Day 1 or placebo (6/2)
4 (8 subjects)	Single oral administration of DNDI-6148, 80 mg on Day 1 or placebo (6/2)
5 (8 subjects)	Single oral administration of DNDI-6148, 160 mg on Day 1 or placebo (6/2)
6 (8 subjects)	Single oral administration of DNDI-6148, 260 mg on Day 1 or placebo (6/2)
7 (8 subjects)	Single oral administration of DNDI-6148, 380 mg on Day 1 or placebo (6/2)
8 (8 subjects)	Single oral administration of DNDI-6148, 500 mg on Day 1 or placebo (6/2)

At each dose level, subjects will be split at least in two sub-cohorts: first sub-cohort will be one subject under active, one subject on placebo (sentinel approach as recommended by EMA[7]). The 6 remaining subjects will be dosed after a minimum of 24 hours of safety surveillance of the first 2 subjects. Decision to proceed with the administration of the 6 remaining subjects will be taken by the investigator on the basis of biology and clinical safety data. The 6 remaining subjects can be divided in multiple subgroups. Any safety data available on previous subjects will be taken into consideration before dosing any new subject. Any concern should be shared with the Sponsor prior to next dosing.

3.3.3.2. Dose Escalation

As the first objective of the study is safety assessment, the dose escalation is designed to progress from the first to the highest planned dose up to the occurrence of relevant events if any.

At the end of each dose level a dose escalation teleconference meeting will be held between the Investigator and the Sponsor representatives, and the decision on how to proceed (e.g. next higher dose) will be taken on the basis of a blind safety and pharmacokinetic data review.

Starting with the lowest dose, each of the subsequent escalating doses will be administered only if the preceding dose was safe and well tolerated. Decision to escalate the dose will be taken during the meeting of the Safety Review Committee described below after reviewing the following data per cohort:

- Blinded Safety data: all data collected over the 4 days for the cohorts 10 mg, 20 mg, 40 mg and 80 mg, or 6 days for the cohorts 160 mg, 260 mg, 380 mg and 500 mg, following study drug administration, for at least 6 subjects, including:
 - Any adverse events reported;
 - All laboratory parameters outside of ranges;
 - Concomitant therapy;
 - o Physical and neurological examination (including VAS and C-SSRS questionnaires);
 - Vital signs;
 - Safety ECG if abnormalities are considered clinically significant by the investigator

All safety data will be presented in an Interim Safety Report issued by the Investigator.

Blinded blood PK data:

- Up to H72 timepoint for the dose escalation from 1st to 2nd cohort for the 6 subjects under active:
- Up to H48 preliminary PK analysis for a minimum of 4 subjects under active for cohorts 40 mg and 80mg
- Up to H120 preliminary PK analysis for a minimum of 4 subjects under active for the cohorts 160 mg, 260 mg, 380 mg and 500 mg
- Blinded Central Reading ECG for a minimum of 6 subjects. ECG central reading data will be presented in a cohort report.

The 3-day surveillance period has been defined based on the predicted half-life of the drug (i.e. sufficient time to determine the terminal half-life and maintain the clinical and biological surveillance up to final drug elimination). Following review of interim results of the 3 first cohorts (10 mg, 20 mg and 40 mg), GM half-life of DNDI-6148 was around 20 hours and five half-lives corresponds to 100 hours. All the volunteers will remain under medical surveillance for 72 hours (presence of a medical doctor in the facility 24h/24 during the hospitalisation of volunteers), and for the cohorts 160 mg, 260 mg, 380 mg and 500 mg, the collection of blood PK samples has been extended up to 120 hours

The study will proceed to the next dose level only if the safety results are acceptable, as agreed by the Safety Review Committee (gathering at least the Sponsor medical responsible, a pharmacokineticist and the Investigator) and if stopping rules are not met. A minimum of 6 subjects per cohort with complete safety data available will be required for decision to proceed to the next dose level (i.e. minimum of 4 subjects under active). All safety data available at the time of the Safety Review Committee meeting will be taken into account for decision on dose-escalation (including safety data from previous cohorts).

At the end of the Safety Review Committee meeting, the following decisions can be taken:

- Dose escalation will continue as scheduled;
- An intermediate dose between the current dose and the following dose will be administered to the next cohort;
- A lower intermediate dose, between the current dose and the dose administered in the previous cohort will be administered to the next cohort;
- The current dose will be repeated in the next cohort;
- The study will be stopped.

According to the conclusion of this meeting, the formal agreement/disagreement will be signed by both the Sponsor and the Investigator.

One cohort can be duplicated to enlarge the number of subjects in one sub-group in case of need. In case the stopping rules are met, no duplication of the same cohort will be possible.

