Prediction of exposure shown in Table 5, based on current knowledge that include both *in vitro* and animal data, show that the PK stopping rules (see § 3.5.3 Dose escalation Stopping criteria between cohorts) are likely to be met before reaching the maximum dose planned in the study if all worse-case scenario hypotheses used for the prediction are met. Because a certain degree of uncertainty on the level of exposure at a given dose remains as no data is available in human, the proposed doses may as well not reach the PK stopping rule defined in the current version of the protocol (due to lower than expected bioavailability, higher elimination rate, shorter half-life, etc.). For this reason, some cohorts have been planned but may actually not be performed. Importantly, at all stages, both actual data providing exposure in humans in the previous cohort and the predictions will be considered for dose-escalation decisions, so that the defined stopping rules are not overpassed, and safety of the subjects is insured.

Moreover, should the PK stopping rules be met at any time but not the safety stopping criteria, the trial will be interrupted and a substantial amendment on the PK stopping rule may be considered, depending on the actual safety data gathered up to that point.

Table 5 Exposure predictions

DNDI-6148	Dose/subject* (mg)	Est. Human C _{max} (ng/mL)	Est. Human AUC ₀₋₂₄ (h*µg/mL)
First cohort dose	10	509	7.68
Last cohort dose**	500	18105	100
Lowest Predicted efficacious dose	16	724	8.81
Highest Predicted efficacious dose	479	17351	96.1

^{*} Dose is based on a 70 kg body weight

Acute toxicity with single drug dosing is not anticipated to pose a risk of concerns to volunteers due to expected limited exposure.

The following single doses of DNDI-6148 are planned to be administered:

^{**} Predicted exposures at worst case scenario may reach Cmax and AUC0-24 stopping criteria set to 7.34 μ g/mL and 64.8 h* μ g/mL based on female monkey 5 mg/kg D28 TK

Table 6 Doses for administration

Dose group	Dose (mg)	Dose (mg/kg*)	Increase from the previous dose
1	10	0.14	
2	20	0.29	+100%
3	40	0.57	+100%
4	80	1.14	+100%
5	160	2.29	+100%
6	260	3.71	+63%
7	380	5.46	+46%
8	500	7.14	+32%

^{*} Assuming a 70-kg person

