3.5.3. Dose escalation Stopping criteria between cohorts

The Safety Review Committee will decide to stop the dose escalation as planned per protocol in case of occurrence of:

- 2 subjects of the same cohort experiencing:
 - a significant increase of ALAT > 3ULN,

- simultaneous increases of total bilirubin > 2ULN, ALAT > 2ULN and alkaline phosphatases > 1.5ULN,
- ➤ 6 subjects of the same cohort experiencing:
 - study drug related moderate, non-serious AEs (that are considered at least possibly related to the drug effect i.e. moderate, non-serious ARs).
- 1 subject of the cohort presenting:
 - a C_{max} or AUC₀₋₂₄ value above 7.3 μg/mL and 65 h*μg/mL, respectively (based on the NOAEL in Cynomolgus toxicology studies).
- The maximum C_{max} and AUC_{0-24} observed in the cohort leads to believe that, taking into account the dose increase, C_{max} or AUC_{0-24} values of 7.3 µg/mL and 65 h*µg/mL might be overpassed with the following planned higher dose.

In one of the cases listed above, the dose group in progress will be stopped and the blind could be broken by the investigator or on request of the sponsor, for one or several volunteers, or the Safety Review Committee could request the support of an independent non-blinded external advisor. Regarding laboratory abnormalities described above, if unblinding confirms that at least two subjects presenting these abnormalities received the active drug, the dose escalation will be stopped.

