3.6. Removal of Subjects from Therapy or Assessment

In accordance with the Declaration of Helsinki, subjects will be free to withdraw from the study at any time if they wish to do so, for any reason, specified or unspecified.

Subjects who withdraw from trial participation before randomization are considered screening failures.

The following reasons will be accepted for study discontinuation:

- Withdrawal of subject consent, or loss to follow-up, or inability to remain under medical observation including post-study examination,
- Non-compliance or major deviation from the protocol,
- Appearance of a serious AE (SAE),
- New significant information (French regulation: "fait nouveau"), any new fact concerning the research or the study product which may jeopardize the participants' safety, and which leads the Sponsor or Investigator to take appropriate urgent security decision,
- Any other situation where, in the opinion of the Investigator, continuation of the study would not be in the interest of the subject,
- Discontinuation of the study by the Sponsor.

Should any of the subjects be withdrawn from the study, the Sponsor's representative and Investigator will discuss the possibility of replacement. All subjects withdrawing for reasons unrelated to the investigational product will have to be replaced. The reason for withdrawal will have to be recorded in the e-CRF for all withdrawn subjects.

The e-CRF has to be completed up to the time of drop out. All drop outs after the first intake of investigational product should be given a post-study assessment as appropriate. The premature termination form in the e-CRF must be completed for all drop outs.

All data, including any drug concentrations from any withdrawn subject, have to be included in the final clinical study report. These data will only be evaluated if both the Sponsor and the Investigator agree that it is valid to do so.

Subjects presenting adverse experiences will undergo a physical examination and laboratory tests planned at the subsequent visits. A follow-up of AEs will also be undertaken for all subjects until resolution or stabilisation of the event.

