11.4. Interim Analysis

Interim PK calculations will be performed at the end of each dose group based on blinded data.

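### From 40 mg upward, escalation may be decided on PK from 4 of the 6 active subjects, although the exposure stopping rule turns on any one subject and on the cohort maximum

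*Protocol*

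**What the plan says.** Each cohort has 6 active and 2 placebo subjects (section 3.2). Section 3.3.3.2 lists the PK to be reviewed before the dose is raised:

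- From cohort 1 to cohort 2: "Up to H72 timepoint for the dose escalation from 1st to 2nd cohort for the 6 subjects under active".
- 40 and 80 mg cohorts: a preliminary analysis to H48 in at least 4 active subjects.
- Higher cohorts: a preliminary analysis to H120 in a "minimum of 4 subjects under active for the cohorts 160 mg, 260 mg, 380 mg and 500 mg".

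The same section says that "All safety data available at the time of the Safety Review Committee meeting will be taken into account for decision on dose-escalation". That sentence covers safety data and does not mention PK.

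Section 3.5.3 sets two exposure rules:

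- Escalation stops with "1 subject of the cohort presenting" a Cmax above 7.3 µg/mL or an AUC0-24 above 65 h*µg/mL.
- It also stops if the maximum "observed in the cohort leads to believe that, taking into account the dose increase", those values might be exceeded at the next planned dose.

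Section 1.4 states the purpose: human exposure data and predictions are considered at every stage "so that the defined stopping rules are not overpassed". Section 11.4 adds that "Interim PK calculations will be performed at the end of each dose group based on blinded data" and gives no number of subjects.

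**The concern.** Both exposure rules depend on the highest exposure in the cohort, so they can be checked fully only if every exposed subject has been seen. The data requirement allows two of the six active subjects to be left out. The look-ahead rule does not close the gap, because its maximum would be taken over the same reviewed subset. The requirement is strictest at 10 mg, where exposure is lowest, and looser at the doses where the limit is more likely to be reached. Section 1.4 itself expects that, under worst-case assumptions, the PK rules may be met before 500 mg.

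At stake is a cohort dosed higher although a stopping rule had been met in a subject whose result was not on the table. Since 500 mg is the last planned dose, the weakness bears on the decisions taken after the 40 to 380 mg cohorts.

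**Working it through.** **The protocol's own figure.** Section 3.3.3.2 requires complete safety data from 6 of 8 subjects and equates this with at least 4 on active. With 2 on placebo, 6 − 2 = 4, so the figure reproduces. The protocol gives no sample size calculation or error rate to check.

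**Step 1: chance that an over-limit subject is unseen, before look-ahead.** Suppose 4 of 6 are reviewed and the other 2 are missing at random. If *k* of the six are over the limit, none of them is seen with probability C(6−k, 4)/C(6, 4):

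- k = 1: 5/15 = 1/3
- k = 2: 1/15 = 6.7%
- k ≥ 3: 0

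**Step 2: add the look-ahead rule.** Let *p* be the probability that a subject is over the limit, *r* the ratio of next dose to current dose (Table 6 of section 1.4), and *m* the number reviewed. With lognormal exposure and proportional scaling, a reviewed subject triggers neither rule with probability

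G = Φ(z₁₋ₚ − ln r / s), where s = √ln(1 + CV²).

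Escalation past a met limit needs all *m* reviewed subjects to pass and at least one of the others to be over the limit:

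share of all cohorts = Gᵐ × [1 − (1 − p)⁶⁻ᵐ].

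The protocol gives no between-subject variability and no exceedance rate. I assumed CV 20%, 30% and 40%, and p = 0.05 and 0.10.

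Worked case, 380 to 500 mg, CV 40%, p = 0.10, m = 4:

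- r = 500/380 = 1.316, ln r = 0.2744, s = √ln 1.16 = 0.3853
- G = Φ(1.2816 − 0.2744/0.3853) = Φ(0.569) = 0.715
- share = 0.7154⁴ × (1 − 0.9²) = 0.262 × 0.19 = 4.98%

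Ranges over the assumed CV and p:

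| Step | r | 4 reviewed | 5 reviewed | 6 reviewed |
|---|---|---|---|---|
| 40 to 80, 80 to 160 mg | 2 | 0.00-0.36% | 0.00-0.08% | 0 |
| 160 to 260 mg | 1.625 | 0.00-1.74% | 0.00-0.58% | 0 |
| 260 to 380 mg | 1.462 | 0.09-3.01% | 0.01-1.15% | 0 |
| 380 to 500 mg | 1.316 | 0.84-4.98% | 0.20-1.90% | 0 |

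A simulation of 400,000 cohorts for the worked case gave 5.03% with 4 reviewed and 1.87% with 5, in line with the formula.

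These are shares of all cohorts. Dividing by the chance that at least one of six is over the limit, 1 − (1 − p)⁶ (26.5% at p = 0.05, 46.9% at p = 0.10), gives the rate among cohorts where the rule was in fact met. At 380 to 500 mg with 4 reviewed this is about 2-17%.

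**Step 3: what a missed subject would mean at the next dose.** A subject just at AUC0-24 65 scales to 65 × 500/380 = 85.5 h*µg/mL at the last step and to 65 × 380/260 = 95.0 at the step before. The limit is the female-monkey NOAEL exposure; the male-monkey value in the same study is 162 h*µg/mL (section 1.4, Table 4).

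**The case against.** The strongest reply is that the protocol already binds the committee. Section 3.3.3.2 lets the study proceed only if the stopping rules are not met, and section 3.5.3 defines those rules over the cohort, not over the subjects reviewed. A committee with six sampled subjects that looked at four would not have shown that the rules are not met. On this reading the 4 is only a floor, matching the safety floor, for incomplete cohorts or incomplete H48 and H120 profiles. If only four active subjects were dosed, there are no unseen ones.

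This establishes the intent, and the floor may well be meant for the long profiles. But no sentence says whose exposures must be known before the rules are declared not met. The only explicit number is 4, and a decision taken on 4 complies with it. The replacement clause (section 3.6: "All subjects withdrawing for reasons unrelated to the investigational product will have to be replaced") deals with withdrawals, not with samples that have not yet been assayed.

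A second reply is that the percentages apply only once a cohort has been reached. With p at the current dose, each of four reviewed subjects at the previous dose would already have triggered look-ahead with probability p, so that step is passed with probability (1 − p)⁴: 81% at p = 0.05, 66% at p = 0.10. Including this factor gives about 0.6-3.7% at 380 to 500 mg and 0.1-2.5% at 260 to 380 mg. That is correct as a per-trial figure; it does not contradict the per-cohort one.

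Third, the consequence is mild. A later non-GLP 29-day monkey study (section 1.2.1.4) set a NOAEL at AUC 264 h*µg/mL in males and 210 in females, and section 1.4 treats the PK limit as open to amendment. This stands, and it supports the view that no harm is expected.

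**Conclusion.** The concern holds and should be fixed. From the 40 mg cohort up, the minimum PK data for escalation do not match stopping rules that turn on any one subject and on the cohort maximum.

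The 1/3 figure needs only that exactly one subject is over the limit and that the two unreviewed subjects are missing at random. The step-by-step percentages also rest on the assumed CV, exceedance rate, lognormal shape and proportional scaling, and on the bare minimum of 4 being used. Within those assumptions the risk is negligible at the doubling steps, and it grows at 260 to 380 and 380 to 500 mg, where the small increments weaken the look-ahead. The issue is a pre-set exposure limit in a first-in-human trial that is not reliably enforced.

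**What to change.** Keep the 4-subject minimum in section 3.3.3.2 for the full H48 and H120 profiles, and add:

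> Cmax and AUC0-24 from every active subject with samples collected to 24 h will be reviewed before the escalation decision; for a subject without a complete 0-24 h profile, all concentrations obtained will be reviewed and the reason for the missing samples documented.

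The second half keeps an early withdrawal or a lost sample from blocking escalation. Sampling to 24 h is already scheduled for every subject (sections 6.2.1 and 8.2.2), so no extra blood is drawn. The cost is one sentence by protocol amendment and possibly a short wait for the last subjects' 0-24 h bioanalysis before the meeting.

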3.4. Expected duration of subject participation

3.4.1. Description and duration of trial periods

For the cohorts 10 mg, 20 mg, 40 mg and 80 mg:

- Screening within 28 days prior to the first administration;
- Hospitalization for 5 days (D-1 morning to D4 morning);
- End of study visit: D4.

For the cohorts 160 mg, 260 mg, 380 mg and 500 mg:

- Screening within 28 days prior to the first administration;

- Hospitalization for 5 days (D-1 morning to D4 morning);
- Ambulatory visits on D5 and D6;
- End of study visit: D6.

Expected duration = approximately 35 days for each subject Expected duration of the trial = 15 months

3.4.2. Duration of follow-up

During the last visit, subjects will undergo a complete clinical and biological examination, identical to the examination at the start of the study. Adverse events (AEs), if any, will be recorded, and if they are ongoing a further follow-up will be arranged; follow-up will continue until the event is resolved or the condition is unlikely to change or the subject is lost to follow-up (see section 8.5). In case abnormal laboratory values are obtain following last samples taken during end of study visit, a further follow-up will also be arranged.

3.4.3 End of study

The last visit of the last subject as scheduled in the protocol will be used to determine the end of study (= Day 4 for the cohorts 10 mg, 20 mg, 40 mg and 80 mg or Day 6 for the cohorts 160 mg, 260 mg, 380 mg and 500 mg).

In case an adverse event or an abnormal laboratory result is in follow-up phase after this date, the end of study would be considered as the date of the last examination performed (e.g.: clinical examination or biological analysis) or the last date of contact in case the follow up is longer than expected and the event is assessed as "chronic" or "stable".

3.5. Stopping rules

3.5.1. Trial stopping criteria

The trial will be stopped if either of the following occurs:

- a 'serious' adverse reaction (SAR) (i.e. a serious adverse event (SAE) considered at least possibly related to DNDI-6148) in one subject; or
- 'severe' non-serious adverse reactions (AR) (i.e. severe non-serious adverse events considered as, at least, possibly related to DNDI-6148) in two subjects in the same cohort, independent of within or not within the same system organ class (SOC).

3.5.2. Stopping criteria within a cohort

During the treatment period, the safety and tolerability will be evaluated on an ongoing basis, the following criteria will apply to stop the dosing in the cohort:

- 2 subjects experiencing severe non-serious AEs considered as at least possibly related to the study drug
- 2 subjects experiencing a significant increase (i.e. > 5 upper limit of normal value [ULN]) of ALAT.

3.5.3. Dose escalation Stopping criteria between cohorts

The Safety Review Committee will decide to stop the dose escalation as planned per protocol in case of occurrence of:

- 2 subjects of the same cohort experiencing:
 - a significant increase of ALAT > 3ULN,

- simultaneous increases of total bilirubin > 2ULN, ALAT > 2ULN and alkaline phosphatases > 1.5ULN,
- ➤ 6 subjects of the same cohort experiencing:
 - study drug related moderate, non-serious AEs (that are considered at least possibly related to the drug effect i.e. moderate, non-serious ARs).
- 1 subject of the cohort presenting:
 - a C_{max} or AUC₀₋₂₄ value above 7.3 μg/mL and 65 h*μg/mL, respectively (based on the NOAEL in Cynomolgus toxicology studies).
- The maximum C_{max} and AUC_{0-24} observed in the cohort leads to believe that, taking into account the dose increase, C_{max} or AUC_{0-24} values of 7.3 µg/mL and 65 h*µg/mL might be overpassed with the following planned higher dose.

In one of the cases listed above, the dose group in progress will be stopped and the blind could be broken by the investigator or on request of the sponsor, for one or several volunteers, or the Safety Review Committee could request the support of an independent non-blinded external advisor. Regarding laboratory abnormalities described above, if unblinding confirms that at least two subjects presenting these abnormalities received the active drug, the dose escalation will be stopped.

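### Section 3.5.3 counts only moderate related AEs, so five moderate plus one severe-only reaction meets no counted AE stopping rule, while six moderate reactions do

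*Protocol*

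**What the plan says.** The counted AE rules stand in three places in the Protocol.

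- **3.5.1 (trial):** one subject with a related serious event stops the trial, and so do related severe non-serious reactions "in two subjects in the same cohort, independent of within or not within the same system organ class".
- **3.5.2 (within a cohort):** dosing in the cohort stops with "2 subjects experiencing severe non-serious AEs considered as at least possibly related to the study drug".
- **3.5.3 (between cohorts):** the Safety Review Committee will stop escalation with "6 subjects of the same cohort experiencing" "study drug related moderate, non-serious AEs". The criterion then restates itself with the same single grade.

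Section 8.3.4.1.1 defines moderate and severe as separate grades. When an event's intensity changes, the source documents keep each change, but the eCRF holds only the maximum.

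Two further consequences follow from meeting a 3.5.3 rule. First, "the dose group in progress will be stopped". Second, under 3.3.3.2, "In case the stopping rules are met, no duplication of the same cohort will be possible".

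Outside the counted rules, 3.3.3.2 also sets conditions of judgement: "each of the subsequent escalating doses will be administered only if the preceding dose was safe and well tolerated", and "The study will proceed to the next dose level only if the safety results are acceptable, as agreed by the Safety Review Committee".

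**The concern.** A stopping rule should not switch off when the outcome gets worse. Here it can. If six subjects have moderate related reactions, 3.5.3 is met. If one of those reactions is severe instead, the moderate count falls to five and the severe count is only one, so neither threshold is reached.

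The liver criteria in the same list do not behave this way. They are open-ended limits, so a worse value still counts. The AE criterion is open-ended for causality (at least possibly related) but tied to one exact grade for severity.

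Each cohort has six active subjects. Unless a placebo subject's event is also judged related, six is therefore the whole active arm, and one active subject with only a severe reaction puts the count out of reach.

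At stake is what the protocol fixes in advance. With six moderate reactions, the end of escalation and the ban on duplicating the cohort are settled. With the worse profile, both depend on the committee's discussion. Repeating the dose, which would expose six more active subjects at the 6/2 split, is then not barred.

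**Working it through.** The protocol has no power or error-rate figure on this point. Its own figures are the thresholds: 1 serious, 2 severe, 6 moderate.

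**Step 1: code the rules.** 3.5.3 counts subjects who experience a moderate AE, not subjects by worst grade. So classify the subjects with related non-serious AEs as:

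- M = moderate only
- S = severe only
- B = severe plus a separate moderate AE

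Rules as written: stop if M + B ≥ 6 or S + B ≥ 2.
Rules with 'at least moderate': stop if M + S + B ≥ 6 or S + B ≥ 2.
Related serious events are outside the comparison, because one already stops the trial.

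**Step 2: find where the two differ.** They differ only if M + S + B ≥ 6, S + B ≤ 1 and M + B ≤ 5.

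- S + B = 0 needs M ≥ 6 and M ≤ 5: impossible.
- B = 1, S = 0 needs M ≥ 5 and M ≤ 4: impossible.
- S = 1, B = 0 needs M ≥ 5 and M ≤ 5: M = 5.

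Enumerating all splits, 84 for six active subjects and 165 for eight cohort members, gives the same single case: (M, S, B) = (5, 1, 0).

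**Step 3: neighbouring cases under the current text.**

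| Moderate only | Severe only | Rule met |
|---|---|---|
| 6 | 0 | 3.5.3 |
| 5 | 1 | none (5 < 6, 1 < 2, serious 0 < 1) |
| 4 | 2 | 3.5.1 and 3.5.2 |
| 6 | 1 | 3.5.3 |

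**Step 4: how often.** The protocol states no AE rates, so these are assumptions. Each of six active subjects independently has a worst related non-serious AE that is moderate (probability m) or severe (s). A subject with a severe reaction also has a separate related moderate AE with probability q. Then

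P(uncovered case) = 6 × m⁵ × s × (1 − q).

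Example: m = 0.50, s = 0.05, q = 0 gives 6 × 0.03125 × 0.05 = 0.0094.

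| m / s | q = 0 | q = 0.5 | q = 0.75 | q = 0.5, two placebo subjects also counted* |
|---|---|---|---|---|
| 0.30 / 0.05 | 0.07% | 0.04% | 0.02% | 0.12% |
| 0.50 / 0.05 | 0.9% | 0.5% | 0.2% | 0.8% |
| 0.50 / 0.10 | 1.9% | 0.9% | 0.5% | 1.5% |
| 0.70 / 0.10 | 10% | 5.0% | 2.5% | 5.4% |
| 0.80 / 0.10 | 20% | 9.8% | 4.9% | 9.1% |

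*Placebo assumed 10% moderate, 0% severe.

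The q = 0 column is the upper value with respect to q. In the last two rows most subjects react, several AEs per subject are plausible, and q = 0 is least credible there.

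**Step 5: effect of the rewording.** At q = 0.5, the chance that some AE count rule is met rises from 5.3% to 5.8% at 0.50 / 0.05, and from 28.2% to 33.3% at 0.70 / 0.10. The whole increase comes from the one split.

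**The case against.** The strongest reply is that the consequence is small, because judgement already covers the case. Section 3.3.3.2 allows escalation only after a safe and well tolerated dose with results that the committee accepts. Six subjects with related reactions of moderate grade or worse plainly engage both conditions. Duplication is foreseen only in case of need, and the Sponsor and the Investigator both sign the outcome of the meeting. This stands. A reader might infer that the trial would escalate automatically after the worse outcome; the protocol does not support that.

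A reader might also infer that the loss of the stop on the dose group in progress leaves subjects exposed. It hardly does. The study is single-dose, so if the six affected subjects are the active ones, all of them have been dosed. If placebo subjects are among the six, at most two subjects remain, and 3.3.3.1 requires available safety data to be considered before any new subject is dosed.

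A third reply is that a reaction which passed through moderate before becoming severe was experienced at moderate grade, and the source documents show it. On that reading the subject counts, and the gap shrinks to reactions that were severe from onset. The reading is tenable, but a count taken from the eCRF would miss such a subject.

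Finally, the thresholds 1, 2 and 6 form a sensible graded scheme. That is true of the numbers, which need no change. It does not explain why a worse outcome should meet fewer rules.

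**Conclusion.** The concern holds as a wording error at one boundary. On the literal text, five moderate-only subjects plus one severe-only subject meet no counted AE rule, while the milder six-moderate case meets 3.5.3. What is lost there is certainty: the mandatory escalation stop and the automatic bar on duplication become discretionary.

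A wider reading, that mixed moderate and severe cohorts generally escape the rules, is not supported: every other split with six or more affected subjects meets a rule.

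The size rests on assumed rates, independence between subjects and the assumed q. It is below about 1% at m = 0.50, s = 0.05, and several percent only if most active subjects have moderate related reactions. The 10% and 20% entries need extreme rates with q = 0 and deserve little weight. The liver and exposure criteria in 3.5.3 could also fire independently. Severity: minor.

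**What to change.** In the six-subject criterion of 3.5.3, replace the AE phrase with: *study drug related, non-serious AEs of at least moderate severity (moderate or severe)*. Make the bracketed restatement that follows it match. Keep the threshold of six, and leave the two-severe rules in 3.5.1 and 3.5.2 as they are.

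The cost is one phrase. The only downside is a mandatory stop in the one additional case, five moderate-only plus one severe-only.
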